6.4.2 Continuous glucose monitoring

From day 1 to day 12, participants will wear a continuous glucose monitor device on the non-dominant upper arm. The FreeStyle Libre Pro iQ (Abbott) is a system that can measure blood glucose profiles reliably over a period of up to 14 days; it is a standard technique in daily diabetes practice. A needle-shaped sensor will be inserted subcutaneously in the skin of the arm. Glucose concentrations will be measured every 15 minutes in the interstitial fluid of the subcutaneous tissue. These values will be sent to a monitor via a transmitter.

After collecting all the data, blood glucose profiles will be examined for readings that deviate from the normal range. If any abnormalities are detected, participants will be notified while maintaining rigorous medical confidentiality.

Fig. 3. Continuous glucose monitor

6.4.3 ECGpro Holter-RR USB

The AMEDTEC Holter ECG (Fig. 4) constitutes a comprehensive long-term ECG system designed with an optimal workflow. It efficiently delivers swift and precise analysis of Holter

ECG recordings, available in either 3 or 12-channel modes. Thanks to the device's Auto-Feedback Logic (AFL), participants experience minimal discomfort. It is capable of recording data for multiple days (up to 72 hours) and can store up to 300 measurements. Furthermore, it enables the definition of various day and night intervals.

Fig.4. ECGpro Holter-RR USB

The ambulatory blood pressure monitoring (ABPM) system AMEDTEC ECGpro Holter-RR, created from the ABPM software Holter-RR, manufacturer: AMEDTEC Medizintechnik Aue GmbH, CE 0494, and the ABPM recorder device Holter-RR, manufacturer: I.E.M. GmbH, CE 0044, is a system according to Directive 93/42/EEC, article 12, and complies with the essential requirements of MDD 93/42/EEC as well as the regulations of the Medical Devices Act. AMEDTEC Medizintechnik Aue GmbH maintains a certified quality management system according to DIN EN ISO 13485 and a certificated quality assurance system according to MDD 93 / 42 / EEC, Annex II.

The Holter-RR NIBP device complies with the requirements of the ESH (European Society of Hypertension) and has a BHS (British Society of Hypertension) A/A grading. AMEDTEC ECGpro Holter-RR is a medical device of risk class IIa by MDD 93/42/EEC, annex IX. The device complies with the requirements of the applicable standards, particularly

- DIN EN ISO 80601-2-30 „Medical electrical equipment –Part 2-30: Particular requirements for the basic safety and essential performance of automated type non-invasive sphygmomanometers“,
- DIN EN 60601-1 „Medical electrical equipment – Part 1: General requirements for basic safety and essential performance“ and

- DIN EN 60601-1-2 „Medical electrical equipment – Part 12: General requirements for basic safety and essential performance – Collateral standard: Electromagnetic disturbances – Requirements and tests“.

After collecting all the data, the heart rate and blood pressure data will be examined for readings that deviate from the normal range. If any abnormalities are detected, participants will be notified while maintaining rigorous medical confidentiality.

6.4.4 iButton thermal skin sensor

A wireless temperature system for human skin temperature measurements is described, i.e. the iButton (type DS1921H; Maxim/Dallas Semiconductor Corp., USA). The iButton is a small (16×6mm²), rugged self-sufficient system that measures temperature and records the results in a protected memory section. Afterwards time and temperature data can be transferred directly to a computer for data analysis. Four iButtons will be worn by participants on day 11 and 12 from 08:30 to 17:00 h, respectively. The four iButtons will be placed on the right foot, left hand, left chest and neck, as shown in Figure 5 below. They will be attached with self-adhesive tape.

[figure not shown]

Fig.5. iButton thermal skin sensors

All sensors that will be applied to the participants (i.e., ActLumus, FreeStyle Libre Pro iQ, iButtons, ECGpro Holter-RR) are CE-certified and will be used only for their intended purpose.

6.5 Flowchart and Schedule

After a person expressed interest in participation, researchers will reply by sending the information letter and consent form via email. Subsequently, researchers will schedule a phone call during which they will provide a brief overview of the key aspects of the experiment and address any questions or concerns which participants may have. Additionally, this phone call will serve as an opportunity to evaluate participants' eligibility based on the inclusion and exclusion criteria (see 6.3.1. phone call screening).

Following the phone call and scheduling the participation days, participants will sign the informed consent form during the first visit at the University Hospital.

On day 1, each participant will undergo an eye examination and thereafter starts wearing the wearable sensors and receives instructions on how to complete the smartphone-based self-report forms are provided. After the ambulatory assessment period in participants' everyday life (days 2-10), participants will spend the 11th and 12th day in a controlled office room environment from 08:30 to 17:00 h. Between day 11 and 12, participants will leave controlled conditions from 17:00 h on day 11 to 08:30 h on day 12.

Throughout these 12 days, the sensors continuously record data until they are removed at the end of day 12. Flowchart 1 illustrates this 12-day study period.

[figure not shown]

Fig.6.: Flowchart of chronological events of participants enrolment in the study.

7 Risks

Overall, the study ensures that participants are exposed to conditions within the naturally occurring limits of daily life. We do not expect any risks from participating in the ambulatory assessment with previous research showing high acceptability and no noteworthy reactivity to measurement in participants' behavior. Nevertheless, on day 11 and 12 participants may be exposed to light conditions that could be perceived as uncomfortable compared to their preferences.

Blood pressure measurements will be performed on day 11 and 12 by means of an automatic inflatable cuff. These measurements might feel a bit uncomfortable, but do not induce negative health effects. After wearing the continuous glucose monitor for 12 days, skin irritation can occur from where the sensor wire is inserted.

The eye examinations bring no special risks for participants. Individuals might feel dazzled for a few seconds after the slitlamp examination, especially after retinoscopy.

In summary, there are no side effects, exposures, or complications associated with this study.

Medical benefits. The study has no direct medical benefit to the participants. However, the results form the basis for suggesting improvements in light exposure behaviour for health purposes and thus provide a basis for aspects of disease prevention and health promotion. In addition, if something abnormal is noted with respect to the eye examination, daily blood

sugar levels and blood pressure, participants will be informed and advised to seek a medical health professional.

Unexpected medical findings. With wearing the continuous glucose monitor and the blood pressure cuff as well as eye examinations, there is a small risk of unexpected medical findings. These unexpected findings could be revealed based on abnormal blood sugar levels (i.e. indicative of type 1 or 2 diabetes mellitus, and hypoglycemia, respectively), or abnormal blood pressure levels (i.e. indicative of cardiovascular issues), or eye degeneration (i.e. for which surgery could be recommended). In case of such unexpected findings, a physician (Institute of Ophthalmology) will inform the individual participant and discuss further steps. Prior to such a conversation, the right of the participant not to know is taken into account.

Dealing with COVID-19-related risks. According to WHO, there is no pandemic situation (*Statement on the Fifteenth Meeting of the IHR (2005) Emergency Committee on the COVID-19 Pandemic*, n.d.).

8 Statistical analysis

8.3 Descriptive statistics

Statistical analysis will be performed using the statistical computer programs SPSS for Mac OS (version 25, IBM) and R Studio for Windows. Descriptive statistics will be reported for all data parameters and will be reported as minimum, maximum, mean, standard deviation (SD) and intraindividual standard deviation (iSD) for data assessed in daily life, and/or standard error of the mean (SEM). As a measure of dispersion, SD will be used for descriptive statistics of the assessed data, while the SEM will additionally be reported for the results of the primary and secondary outcomes.

In case of non-normality, values will either be transformed using log transformation or non-parametric tests will be used. In addition, Pearson correlation coefficients will be computed to correlate parameter values. The unpaired Students t-test will be used to compare outcome measures between the young and old group. Due to the randomized cross-over design, to compare outcomes between the bright and dim office light condition irrespective of age (secondary outcome), a paired t-test will be conducted. Differences will be considered statistically significant when tested two-sided $p < 0.05$. Missing values will not be replaced. We will apply a full information approach using all available data from all participants.

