4.4. Registration

The study will be registered on osf.io.

5. Participants

30 healthy younger adults and 30 healthy older adults.

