5.3. Scheduling

The 12 days of testing will take place after an initial phone call screening. Participants can leave the study at any time for any reason if they wish, without any consequences. The investigator may decide to remove a participant from the study for urgent medical reasons. Participants may be removed from the study if they do not adhere to the study procedure. After elimination, there is no follow-up examination of the participant. In case of withdrawal due to medical complications, the participant is referred to a general practitioner.

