8.4 Primary and secondary study parameters

As the primary hypothesis of this study is that younger and older individuals differ in their light exposure patterns in everyday life, the primary outcome of this study is melanopic equivalent daylight illuminance (M-EDI) quantified in lux by the Actlumus wearable light sensor. M-EDI may differ between groups with respect to overall daily levels, exposure levels at different times of day (work-day vs. weekend-day), and the difference in exposure levels between work-days and weekend-days. Therefore, M-EDI will be statistically analysed between groups in the following three ways:

1. Compare the area under the curve (AUC) of M-EDI from day 1 to day 8 between young and old (unpaired t-test)

2. Averaging exposure levels over work-days and weekend-days in 1-hour time intervals over 24 hours and compare the two average 24-hour M-EDI patterns between young and old (2-way repeated measures ANOVA, factor 1 (between-subjects) group, factor 2 (within-subjects) time)
3. Averaging the onset of M-EDI in the morning hours and the offset in the evening over work-days and weekend-days and calculate the difference in onset and offset between the averaged work-day and weekend-day between groups (unpaired t-test)

The secondary hypotheses are that light exposure patterns in everyday life are linked to daily metabolic, cardiovascular and psychological outcomes, and that this link is stronger in individuals displaying less degeneration of eye structures.

Accordingly, mixed effects regression analyses will be performed to assess the relationship between different aspects of daily light exposure (momentary M-EDI, average daily exposure level, onset/offset; independent variables) and each of the daily health parameters (metabolic, cardiovascular, psychological functioning, and sleep; dependent variables). To evaluate the role of the degree of eye degeneration, an interaction term between light exposure and eye degeneration will be added to the regression models.

9 Ethics

The study must be approved by the Ethics Committee of RWTH Aachen University. The study is carried out in accordance with the Declaration of Helsinki (the latest version, established in Fortaleza, Brazil, 2013) and the Law on Medical Research involving Human Beings (WMO) and the General Data Protection Regulation (GDPR or GDPR).

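### Section 8.3 fixes the pooled-variance t-test for young-old comparisons; naming Welch's test would protect the error rate if spread and analysed group size both differ, at almost no cost

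*Protocol*

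**What the plan says.** Section 8.3 sets the general rule for comparing the age groups: "The unpaired Students t-test will be used to compare outcome measures between the young and old group". Testing is two-sided at 5%. The only fallback is for the shape of the distribution: "In case of non-normality, values will either be transformed using log transformation or non-parametric tests will be used". No alternative is given for unequal variances. Missing values are not replaced.

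Section 8.4 lists three primary analyses of melanopic EDI:

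- Item 1 reads "Compare the area under the curve (AUC) of M-EDI from day 1 to day 8 between young and old (unpaired t-test").
- Item 2 is not a t-test but a "2-way repeated measures ANOVA, factor 1 (between-subjects) group, factor 2 (within-subjects) time".
- Item 3 is to "calculate the difference in onset and offset between the averaged work-day and weekend-day between groups (unpaired t-test").

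Items 1 and 3 do not repeat the word Student, but 8.3 supplies it.

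Section 5 plans "30 healthy younger adults and 30 healthy older adults". Section 5.3 allows withdrawal at any time and adds: "Participants may be removed from the study if they do not adhere to the study procedure".

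**The concern.** Student's test estimates one common variance for both groups. In a randomised comparison that assumption holds under the null hypothesis of no effect at all. Here the groups are people aged 18-35 and people aged 60-80, and the protocol gives no SDs and no argument that light exposure, or the shift between work-days and weekend-days, varies equally in both.

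Unequal spread alone does little harm while the groups are the same size. The analysed sizes can drift apart, however. Participants may withdraw or be removed (5.3), missing values stay missing (8.3), and the day-1 eye findings are checked against the exclusion criteria after consent (6.3.1 and 6.3.2), a step likely to affect the older group more. If size and spread both differ, the pooled standard error is wrong. It is too small when the smaller group is the more variable one, which gives too many false positives. It is too large in the opposite case, which makes the test conservative and costs power. Two of the three primary analyses, and any other age contrast that falls under the general rule in 8.3, depend on it.

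**Working it through.** **Inputs from the protocol.** Planned sizes 30 and 30 (section 5 and 6.2); two-sided 5% level and Student's test (8.3); an effect of about d = 0.7 said to be detectable with 30 per group (6.2), with no power stated.

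**Assumed, because the protocol gives neither.** SD ratios of 1, 1.5, 2 and 3, and analysed sizes between 30 v 30 and 20 v 30, with 15 v 30 as an extreme. Data are normal.

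**Step 1: the plan's own figure.** With 30 per group, equal SDs and d = 0.7, Student's test has 76.0% power (noncentral t). There is no stated power to confirm or refute; this serves as the baseline for the cost of a change.

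**Step 2: why both conditions are needed.** Student's squared standard error has expectation

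[((n₁−1)σ₁² + (n₂−1)σ₂²) / (n₁+n₂−2)] × (1/n₁ + 1/n₂),

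whereas the true variance of the difference in means is σ₁²/n₁ + σ₂²/n₂. With SDs of 2 and 1:

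- 30 v 30: pooled (29×4 + 29×1)/58 × 2/30 = 2.5 × 0.0667 = 0.1667; true 4/30 + 1/30 = 0.1667. They agree.
- SD 2 in the group of 20, SD 1 in the group of 30: pooled (19×4 + 29×1)/48 × 0.0833 = 2.1875 × 0.0833 = 0.1823; true 4/20 + 1/30 = 0.2333. Ratio of standard errors √(0.1823/0.2333) = 0.88, so too small.
- SD 2 in the group of 30, SD 1 in the group of 20: pooled (29×4 + 19×1)/48 × 0.0833 = 2.8125 × 0.0833 = 0.2344; true 4/30 + 1/20 = 0.1833. Ratio √(0.2344/0.1833) = 1.13, so too large.

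With equal SDs the two expressions coincide at any sizes, and the simulated error rate stays at 5.0%.

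**Step 3: error rate of Student's test at nominal 5%.** Simulation with 100,000 to 400,000 runs per scenario, checked by numerical integration over the two sample variances.

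| Sizes | Which group is more variable | SD ratio 1.5 | SD ratio 2 | SD ratio 3 |
|---|---|---|---|---|
| 30 v 30 | either | 5.0% | 5.1% | 5.3% |
| 27 v 30 | smaller | 5.6% | 6.0% | 6.3% |
| 25 v 30 | smaller | 5.9% | 6.5% | 7.2% |
| 20 v 30 | smaller | 7.0% | 8.3-8.5% | 10.1% |
| 25 v 30 | larger | 4.3% | 4.0% | 3.8% |
| 20 v 30 | larger | 3.5% | 2.8-2.9% | 2.4% |

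At 27 v 30 with the larger group more variable and SD ratio 2, the rate is 4.5%. The ranges at 20 v 30 are differences between runs; the integration gives 8.5% and 2.9%. In these scenarios Welch's test stays between 4.9% and 5.1%.

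**Step 4: power when the larger group is more variable.** SDs 2 and 1, true difference 1.2, Student v Welch: 76% v 80% (30 v 24) and 70% v 78% (30 v 20).

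**Step 5: cost of Welch when SDs are equal.** d = 0.7, Student v Welch: 76.0% v 75.9% (30 v 30), 71.8% v 71.7% (30 v 25), 66.2% v 65.8% (30 v 20) and 58.1% v 57.0% (30 v 15).

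**The case against.** The strongest reply is that the plan as designed has no problem. The groups are planned at 30 and 30, and there Student's test keeps its level even if one SD is three times the other. That stands. The larger distortions need a loss of about 10 participants from one group and none from the other, in a 12-day study that pays its participants; the protocol predicts nothing of the kind. With a modest imbalance of 27 v 30 the error rate moves by about one percentage point at most for an SD ratio of 2. That stands too.

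The fallback in 8.3 also weakens the concern. The background section describes light levels from about 300 lux in offices to 100,000 lux outdoors, so the light AUC in item 1 is an obvious candidate for the log transformation, which often evens out spread as well. This is a partial answer: the trigger is non-normality, not unequal variance, and a log scale would not necessarily help the onset and offset differences in item 3. Nor does item 3 by itself threaten equal sizes, since any seven consecutive days contain weekdays and a weekend; only substantial non-wear, or a definition of work-day tied to employment, would remove people.

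A reader might infer that every young-old comparison is affected. The protocol does not support that: item 2 is a repeated measures ANOVA, the links between light and health are analysed by mixed-effects regression, and non-normal outcomes leave the untransformed t-test. A reader might also infer that unequal spread or unequal size alone distorts the p-values. Step 2 shows that material distortion needs both.

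Finally, details of variance handling often belong in an SAP. Here, though, the protocol names the pooled form itself, so the point concerns a stated method and not a missing detail.

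**Conclusion.** The point holds as a small robustness improvement. Section 8.3 commits to a pooled-variance test for two different populations, with no support for equal spread and with routes by which the analysed sizes can become unequal. At the planned sizes this does no harm. If the more variable group ends up smaller, then under an assumed SD ratio of 2 the 5% test runs at about 6.0% to 6.5% for losses of 3 to 5 participants, and 8.3-8.5% for a loss of 10. If the more variable group ends up larger, it runs at about 4.5% to 4.0% and 2.8-2.9%, with some loss of power. The direction cannot be foreseen from the protocol.

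All these figures rest on assumed SD ratios, assumed losses from one group only, and normal data. They do not show that the planned analysis is wrong, and figures from more extreme imbalance, such as 15 v 30, should not be used to suggest it.

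**What to change.** In 8.3, and in items 1 and 3 of 8.4, name Welch's unequal-variance t-test. Use it unconditionally, without a preliminary test of variances. Where the plan's log transformation is used, apply Welch's test on the log scale. Report the group difference with its Welch 95% confidence interval.

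The change is a few words, and both programs named in 8.3 provide the test. With equal SDs the price in power is about 0.1 percentage points at 30 v 30, 0.4 at 20 v 30 and 1 at 15 v 30. The repeated measures ANOVA in item 2 is not affected by this change; its own between-group variance assumption stays as it is.

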This study is designed as an observatory field study of characterizing younger and older adults' everyday life in terms of light exposure patterns as well as cardiovascular, metabolic and psychological health parameters over 10 days continuously through wearables and smartphone-based self-reports (ambulatory assessment period). On the first day of data collection, each participant will undergo an eye examination at the Institute of Ophthalmology. Thereafter participants start wearing the wearable sensors and instructions on how to complete the smartphone-based self-report forms are provided. Data will be collected from the first evening onwards (ca. 18:00 h). After the ambulatory assessment period under free-living conditions, participants will spend the 11th and 12th day in a controlled office room environment from 08:30 to 17:00 h. In a randomized cross-over design, the 11th and 12th day will be spent in either bright (1250 lux) or dim office lighting (10 lux). On these days, participants will continue to wear the wearables and complete the same smartphone-based self-reports as over the 10-day ambulatory assessment period. Between day 11 and 12, participants will leave controlled conditions from 17:00 h on day 11 to 08:30 h on day 12. On day 11 and 12, participants will receive a standardized fluid meal for breakfast and a bread-based meal for lunch, and are otherwise instructed to avoid any food, caloric or caffeinated beverages between 08:30 and 17:00 h. After removing all wearables on day 12, the study ends at 17:30 h. Over these 12 days of data collection, participants will be asked to keep their bedtimes at home as consistent as possible between days, and on day 11 and 12 they will be instructed to come to the office facilities fasted without any caloric intake after 22:00 h on the previous evening of day 10 and 11, respectively.

To minimize the burden on participants in this study, we use mobile and user-friendly devices for data collection and give clear instructions for data collection. We keep individual assessments short, limit the study duration to 12 days and provide incentives for participation (up to €200 reimbursement). On day 11 and 12, participants are mostly free to do whatever they like to do while being in the office environment (e.g. watching movies, paperwork, reading, video-meetings etc.).

[figure not shown]

Fig.1. Overview of study design.

4. Responsibilities

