6.4 Measurement devices

All measurements within the framework of the research project are non-invasive, except for placing a continuous glucose monitor on the non-dominant forearm of participants from day 1 of the data collection period onwards.

Table 3 shows the different types and respective resolutions of the recorded data.

The continuous glucose monitor and the light sensor will be worn throughout the 12 days of the study, while the thermal skin sensors and the ambulatory blood pressure device will only be worn on day 11 and 12, between 08:30 and 17:00 h respectively.

Table 3. Data collected, methods and resolution.

Data	Unit	Device name	Frequency
Skin temperature	°C	iButtons	1 min
Interstitial glucose	mmol/L	Abbott Freestyle Pro IQ	15 min
Illuminance	Lux Melanopic EDI	Actlumus	1 min
Blood pressure	mmHg	ECGpro Holter-RR USB	15 min

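### The bright-versus-dim crossover is analysed by a paired t-test that ignores order, so any day-11 to day-12 shift costs power and, if the two orders are unequal in number, biases the estimate

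*Protocol*

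**What the plan says.** Section 3 sets a randomised crossover: one office day in bright light (1250 lux) and one in dim light (10 lux), on days 11 and 12, from 08:30 to 17:00 h. Section 6.5 describes the interval: "Between day 11 and 12, participants will leave controlled conditions from 17:00 h on day 11 to 08:30 h on day 12". For the study period, including that night, section 3 says that "participants will be asked to keep their bedtimes at home as consistent as possible between days". It also asks for no calories after 22:00 h before each office day and gives the same types of breakfast and lunch on both days.

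On devices, section 6.4 states that "the thermal skin sensors and the ambulatory blood pressure device will only be worn on day 11 and 12", whereas "The continuous glucose monitor and the light sensor will be worn throughout the 12 days of the study". The smartphone self-reports on the office days are those of the preceding ambulatory period (section 3).

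On analysis, section 8.3 says: "to compare outcomes between the bright and dim office light condition irrespective of age (secondary outcome), a paired t-test will be conducted". Tests are two-sided at 0.05 and missing values are not imputed. The mixed models in section 8.4 concern daily light exposure and health parameters and name no period or sequence term. The protocol says that the order is randomised but gives no ratio or blocking.

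**The concern.** A two-period crossover has two systematic sources of within-person change: the condition and the day. Randomised order lets the analysis separate them, and the paired t-test does not use it.

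A day effect is plausible here. For blood pressure and skin temperature, day 11 is the first day on which the devices are worn, and section 7 acknowledges that cuff measurements may be uncomfortable. For other outcomes, day 11 is the first day under the office protocol. If readings drift between the days for such reasons, the drift adds to the difference of everyone who had bright light first and subtracts from that of everyone who had dim light first.

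Two things are at stake. One is the precision of the bright-versus-dim comparison and, if the orders are unequal, its freedom from bias. The other is any use of a person's own bright-minus-dim difference as a measure of light sensitivity. The German summary gives this as the purpose of the office days, and section 2 makes the determinants of sensitivity one of two main goals. Balancing the orders does not remove the day effect from an individual's difference.

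**Working it through.** **The plan's own figure.** The only sample-size statement (section 6.2) is 30 per group for d of about 0.7 between age groups, with no power stated. At two-sided 0.05 that gives 76.0% power by the t-test (77.4% by the normal formula). It does not concern the crossover, for which the protocol states no effect, power or sample size.

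**Inputs from the protocol.** 30 + 30 = 60 participants, so N = 60 differences if all complete; two-sided alpha 0.05; two consecutive days in random order.

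**Assumptions.** The shift π (day 11 minus day 12, in units of the SD of the within-person difference) is set to 0.25, 0.5, 0.75 and 1. The light effect δ is set so that the paired t-test has 80% power at π = 0, which gives δ = 0.368.

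**Model.** Bright minus dim for person i is D_i = δ + s_i·π + e_i, with SD(e) = 1, s = +1 if bright came first and −1 if dim came first. Let n1 and n2 be the numbers in the two orders.

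**Step 1: equal orders (30:30).** The mean of D is δ + π·(30 − 30)/60 = δ, so there is no bias. The SD that the paired t-test estimates is about √(1 + π²) instead of 1. Approximate power is Φ(δ√N − t·√(1 + π²)), with δ√N = 0.368 × 7.746 ≈ 2.85 and t = 2.00 on 59 df. For example, at π = 0.5, Φ(2.85 − 2.00 × 1.118) = Φ(0.61) ≈ 73%.

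| π | SE inflation √(1 + π²) | Power, paired t | Power with period term |
|---|---|---|---|
| 0 | 1.00 | 80% | 80% |
| 0.25 | 1.03 | 78% | 80% |
| 0.5 | 1.12 | 73% | 80% |
| 0.75 | 1.25 | 64% | 80% |
| 1 | 1.41 | 51% | 80% |

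Simulation with 20,000 trials per setting agrees: 77.8%, 72.6% and 50.7% for the paired test at π = 0.25, 0.5 and 1, against 79.8% with the period term throughout. The paired test's type I error falls to 4.5%, 2.9% and 0.6%, so it is conservative.

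**Step 2: unequal orders.** The paired mean is biased by π·(n1 − n2)/N:
- 33:27 gives 6/60 = 0.10π
- 35:25 gives 10/60 = 0.17π
- 36:24 gives 12/60 = 0.20π

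At 36:24 the simulated type I error of the paired test is 6.0%, 7.9% and 11.1% at π = 0.25, 0.5 and 1. With the period term it is about 5.1%, with power 78.0%. If the order were assigned by simple 1:1 randomisation (an assumption), 36:24 or worse would occur with probability 16%.

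**Step 3: individual differences.** If D_i were correlated with another measure without regard to order, the correlation would shrink by 1/√(1 + π²): 0.97, 0.89, 0.80 and 0.71 at π = 0.25, 0.5, 0.75 and 1.

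**The case against.** The strongest reply is that the paired t-test is not invalid. With equal orders it is unbiased and errs on the conservative side. Averaged over simple randomisation its type I error stays near 5% (4.9%, 4.9% and 5.0% at π = 0.25, 0.5 and 1). Bias appears only given a realised imbalance, and blocking may be specified in a document not shown. For modest shifts the loss is small: two percentage points of power at π = 0.25. All of this stands. It limits the size of the point but gives no reason to leave out a known design factor.

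Four stronger readings are tempting and are not supported:

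- **All devices are new on day 11.** Section 6.4 limits this to the blood pressure device and skin sensors. The glucose monitor is worn from day 1 and self-reports also start before day 11, so for those outcomes only the novelty of the office day remains.
- **The night between is wholly uncontrolled.** Section 3 asks for consistent bedtimes and fasting after 22:00 h. Light that evening is not controlled.
- **The 15.5 h interval is the problem, and a period term cures it.** A period term does not remove unequal carry-over of bright and dim light. Nor would the light record from 17:00 to 08:30 h settle the matter: section 6.4.1 says that the logger comes off at night, and exposure by first condition does not test carry-over in the outcomes.
- **The planned eye-degeneration results are attenuated.** Section 8.4 plans an interaction of light exposure with degeneration in mixed models, not a regression on the bright-minus-dim difference. The factors in step 3 apply only if that difference is used.

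**Conclusion.** The point holds as a cheap and specific improvement to one secondary comparison. Section 8.3 itself fixes the paired t-test, so this is not a detail left for later. With equal orders the harm is lost power: from 80% to about 78%, 73%, 64% and 51% at shifts of 0.25, 0.5, 0.75 and 1 SD of the within-person difference. With unequal orders the estimate is also biased by π·(n1 − n2)/N given the realised split. The shift, the 80% baseline and the split are all assumptions. The larger losses need a shift of 0.75 to 1 SD, for which the protocol gives no evidence either way. The first-wear argument supports a shift most directly for blood pressure and skin temperature. A reader might infer that the crossover result would be invalid or the study's main conclusion at risk. Neither follows: the test keeps its level on average over simple randomisation, and the primary M-EDI analysis does not use this comparison.

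**What to change.** In section 8.3, replace the paired t-test with a mixed model that has light condition and period (day 11 or day 12) as fixed effects and participant as random effect. With complete pairs the same answer comes from comparing the day-11 minus day-12 differences between the two sequences. Their expectations are π + δ (bright first) and π − δ (dim first), so half the difference is δ and the shift drops out.

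In any analysis that uses the individual bright-minus-dim difference as light sensitivity, include sequence as a covariate.

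State that the period term does not address unequal carry-over, and do not present the overnight light record as a test for it.

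The cost is a change of wording and one degree of freedom (58 instead of 59), with no new data. At 30:30 and no shift, power is 79.8% with either analysis. At 36:24 and no shift it is 78.0% with the period term against 79.8% without.
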